## 5. DURATION / TIMELINE OF THE STUDY

Study start date: 09/2025

Enlistment End Date: December 2025

Data analysis end date: 07/2026

Final Study Report: 08/2026

## 6. STATISTICAL ANALYSIS

### 6.1 Sample size

The total number of samples for which Whole Genome Sequencing (WGS) is planned is 2,880, including 800 subjects with advanced MASLD, 2,000 controls with at least two characteristic criteria of metabolic syndrome but free of advanced liver disease, and 80 liver tissue samples for somatic variant analysis. The sample size estimate is based on the study's primary objective, which is the identification of genetic variants (germline and/or somatic) associated with MASLD.

The study is descriptive with a power proportional to the number of subjects included.

This number was defined on the basis of the maximum availability of subjects that could be enrolled in the clinical cohorts with the aim of maximizing the statistical power and scientific value of the results. Preliminary data on common variants are available that confirm the statistical power of the cohort to identify phenotype-associated variants at the genome-wide level..

To confirm the adequate statistical power of the study, an analysis was performed using the R statistical analysis software package called "genpwr" by setting the error at a significance level of  $5 \times 10^{-8}$  conventionally used to define significance at the genomic level (<https://cran.r-project.org/web/packages/genpwr/index.html>) and the number of cases and controls in the detective cohort. This method is based on an extension of that reported by Gauderman (2002) (doi:10.1093/aje/155.5.478) and Gauderman (2002) (doi:10.1002/sim.973) and described in: Moore CM, Jacobson S, Fingerlin TE. Power and Sample Size Calculations for Genetic Association Studies in the Presence of Genetic Model Misspecification. American Society of Human Genetics. October 2018, San Diego. For common variants, combinations with variant allelic frequency (MAF)  $\geq 0.1$  and OR  $\geq 2.0$  were considered, while for low-frequency and rare variants with a greater impact on protein function, for which the focus is on identifying variants with a greater impact on disease risk, MAF values between 0.01 and 0.05 and ORs up to 15 were explored. The results confirm that based on the expected number of 800 cases and 2000 new controls (without considering the 1000 controls already available) the study will have a power greater than 95% to detect ORs  $> 2$  for common variants with a frequency of 0.1 (power  $> 80\%$  for OR 1.3 for variants even with a frequency of 0.1, and much greater power for even more frequent variants, Graph 1). Furthermore, for low-frequency and rare variants, it will have a

power greater than 80% to detect ORs already  $> 5$  for variants with MAF 0.01 that are difficult to type with array-based methods (see Chart 2), although variants with ORs  $> 8$  are typically expected in this case, for which it will be possible to identify rare variants typeable only with WGS approaches, on which the DETECTIVE study is focused. Furthermore, a preliminary GWAS analysis that considered only common variants typed with Illumina GSA3.0 arrays using fibrosing steatohepatitis defined by Fibrotic NASH Index (FNI) as the main outcome (Chart 3), conducted in a part of the cohort that will be the subject of the study (N=2300) not only confirmed the impact of the two major loci for steatohepatitis already known in the literature (PNPLA3 and TM6SF2), but also highlighted the presence of two new loci not yet described, further strengthening the robustness of the proposed study.

[figure not shown]

Figure 1. Statistical power to identify significant genomewide associations as a function of the OR for different minor allelic frequencies (MAF) of common variants in the Detective cohort

[figure not shown]
[figure not shown]

Figure 2. Statistical power to identify significant genomewide associations as a function of the OR for different MAFs of low-frequency/rare variants in the Detective cohort.

Graph 3. Manhattan plot showing the preliminary results of a genomewide association study (GWAS) for common variants in a first part of the Detective cohort (FOGS Study) using as an outcome the risk of fibrosing steatohepatitis assessed by FNI score. The results were obtained using genomic regression models adjusted for age, sex, body mass index (BMI), presence of diabetes and ethnic background (assessed by principal components PC 1-10).

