#### 4.3 Sample analysis

The genetic analyses for this study will be conducted in close collaboration and under the supervision of Human Technopole.

As anticipated, the methodology envisaged for conducting this study involves whole-genome sequencing on DNA derived from peripheral blood (20x coverage) and pathological liver tissue (50x coverage) to characterize the genetic and somatic variants that influence disease progression.

The DNA will be isolated at the Foundation and shipped to the National Facility (NF) in batches of 3-4 plates at a time.

To identify associations between individual genetic variants and the burden of likely loss-of-function (LoF) variants at specific genetic loci, comparing participants with advanced MASLD to controls, analyses will be performed using a genome-wide regression model implemented in REGENIE, with additive genetic models accounting for age, sex, body mass index (BMI), and ancestry (BWI 1-10). To ensure the robustness of the results, the genome-wide significance threshold will be set at  $p < 5E-8$ . If the study is not powered to identify new significant associations, suggestive hits ( $p < 5E-6$ ) will be replicated in additional cohorts.

In addition to defining the risk of advanced MASLD compared to controls as the primary outcome, we will thoroughly examine the genetic contribution to various endophenotypes. These will include metabolic risk factors (such as insulin resistance indices), liver enzymes (AST, ALT, GGT), and indicators of liver damage (noninvasive predictors of steatosis, steatohepatitis, fibrosis, cirrhosis, and HCC). The results of these analyses will be crucial for improving risk stratification and identifying specific disease subphenotypes through the development of polygenic risk scores, which have previously proven effective in identifying subsets of patients at specific risk for liver or cardiovascular events. This approach will also aim to identify therapeutic targets with a high probability of clinical success.

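### Section 6.1 claims power above 80% for OR 1.3 at allele frequency 0.1; its own inputs give under 1%

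*Protocol*

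**What the plan says.** Protocol section 6.1 reports a power analysis with the R package genpwr, run at a "significance level of $5 \times 10^{-8}$ conventionally used to define significance at the genomic level". The counts are "based on the expected number of 800 cases and 2000 new controls (without considering the 1000 controls already available"). Section 4.3 uses the same limit for the analysis ("the genome-wide significance threshold will be set at" p < 5E-8) and specifies additive genetic models.

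For common variants, section 6.1 says the combinations considered had MAF of at least 0.1 and OR of at least 2.0. It then makes two statements for frequency 0.1:

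- power above 95% for OR above 2;
- in a bracket that refers to Graph 1, power above 80% "for OR 1.3 for variants even with a frequency of 0.1, and much greater power for even more frequent variants".

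The caption of Figure 1 reads "Statistical power to identify significant genomewide associations as a function of the OR for different minor allelic frequencies (MAF) of common variants", so the graph is presented as power at the genome-wide level. No other significance level is given for the power analysis.

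**The concern.** An odds ratio of 1.3 is a modest effect, and 5E-8 is a very strict threshold. With 800 cases, power above 80% at frequency 0.1 is implausible on its face. The bracket also cannot come from the run described, because that run is said to start at OR 2.0.

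The paragraph exists to confirm that the study is adequately powered. A reader, including an ethics committee, would conclude that common variants with OR 1.3 are detectable at the primary threshold. A null result for modest common-variant effects could then be misread as evidence that such effects are absent.

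**Working it through.** **Inputs.** From section 6.1: alpha 5E-8, 800 cases, 2000 controls, OR 1.3, allele frequency 0.1. From section 4.3: additive model. Assumed: two-sided test, Hardy-Weinberg proportions, no covariates. The protocol does not say whether MAF is the frequency in controls or in the pooled sample, so both are shown.

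**Method.** Likelihood-ratio test (LRT) of the per-allele effect in logistic regression. The noncentrality (ncp) is 2N times the difference in expected log-likelihood per subject between the additive and null models, with N = 2800 and case share 800/2800 = 0.2857. Power is the upper tail of the noncentral chi-square (1 df) beyond the critical value. The two-sided normal critical value at 5E-8 is 5.451, so 80% power needs ncp = (5.451 + 0.842)² = 39.60.

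**Step 1: reproduce the neighbouring claim (OR 2.0, MAF 0.1).** ncp is 54.7 (pooled) or 66.0 (control), giving power of 97.4% or 99.6%. This agrees with the stated figure of more than 95%.

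**Step 2: the bracket (OR 1.3, MAF 0.1).** ncp is 7.46 (pooled) or 7.95 (control), giving power of 0.33% or 0.43%. The ncp falls short by a factor of 39.60/7.46 = 5.31 or 39.60/7.95 = 4.98. That is the multiple of the sample needed for 80% power at the same case-control ratio.

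**Step 3: hand check with the allelic test (control MAF).**

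- Case allele frequency: 1.3 × 0.1 / (1 + 0.1 × 0.3) = 0.1262; difference from controls 0.0262.
- Alleles: 1600 in cases, 4000 in controls; pooled frequency (1600 × 0.1262 + 4000 × 0.1)/5600 = 0.1075.
- Null SE: √[0.1075 × 0.8925 × (1/1600 + 1/4000)] = 0.00916.
- Alternative SE: √[0.1262 × 0.8738/1600 + 0.1 × 0.9/4000] = 0.00956.
- z = (0.0262 − 5.451 × 0.00916)/0.00956 = −2.48, so power is 0.65%.

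Simulation of the trend test (400,000 replicates) gives 0.52% (pooled) and 0.67% (control).

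**Step 4: more frequent variants (additive LRT, 5E-8).**

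| MAF | Power at OR 1.3 | OR with 80% power |
|---|---|---|
| 0.1 | 0.33% to 0.43% | 1.74 to 1.81 |
| 0.2 | 3.3% to 4.0% | 1.55 to 1.57 |
| 0.3 | 9.0% to 10.0% | 1.48 to 1.49 |
| 0.4 | 13.7% to 14.5% | 1.46 |
| 0.5 | 15.0% | 1.46 |

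The maximum over MAF at OR 1.3 is 15.3%.

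**Step 5: other readings (OR 1.3, MAF 0.1).**

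- One-sided allelic test: 0.91%.
- Dominant model: about 0.2%. Recessive model: about 0%.
- Adding the 1000 existing controls: 0.54% to 0.66% (additive LRT), 1.1% (allelic).
- Suggestive threshold of 5E-6: 3.3% to 4.1% (additive LRT).
- Alpha 0.05: 78.0% to 80.5%.

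If instead the printed OR were a slip for 1.8, power at 5E-8 would be 78.7% to 90.3%. The last two readings come near the stated figure, but nothing in the protocol supports either, and under the pooled convention both fall just short of 80%.

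**The case against.** The strongest case against concerns weight. Section 6.1 calls the study descriptive and says its size was set by maximum availability. The bracket qualifies a headline claim that holds, and the stated focus is on rare variants rather than common ones. Section 4.3 already foresees low power by sending suggestive hits at 5E-6 to replication. All of this stands and limits the harm, but none of it makes the number true. Even at 5E-6 power is only a few percent.

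The cause is unknown. If the graph is right and the text has a misprinted OR, the power work itself may be sound. That stands too, and the sentence would still need correction.

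The allele-frequency convention also matters. For the protocol's rare-variant statement (power above 80% for OR above 5 at MAF 0.01), the same method gives 99.8% at OR 5 with control MAF but 65.6% with pooled MAF. So the pooled convention does not reproduce that statement at its boundary, and the range 1.74 to 1.81 spans two conventions of which the protocol names neither. The conclusion about OR 1.3 is the same under both.

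Finally, 0.33% to 0.43% is one approximation. Across test forms with the stated inputs the values run up to 0.91%, so under 1% is the safe wording. Adjustment for age, sex, BMI and ancestry is not modelled, but it could not plausibly lift power from under 1% to 80%.

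**Conclusion.** The concern holds with high confidence. The stated power above 80% for OR 1.3 at frequency 0.1 is under 1% with the section's own alpha and counts, under every test form and genetic model tried. The added remark about more frequent variants fails as well. The result assumes Hardy-Weinberg proportions and no covariates; sidedness and the MAF convention do not change it. Separately, and without any calculation, OR 1.3 contradicts the grid the section describes.

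The damage is confined to the stated detectable effect. The claim for OR above 2 stands. This should be fixed, but it does not threaten the design.

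**What to change.** Rerun genpwr at 5E-8 with 800 cases and 2000 controls, and check the output against Graph 1. Then:

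- Replace the bracket with the OR that has 80% power. The values here are about 1.74 to 1.81 at MAF 0.1, about 1.5 at MAF 0.3 and 1.46 at MAF 0.5, to be confirmed by the genpwr run. Either drop OR 1.3 or report its power as under 1% at MAF 0.1.
- Say whether MAF means the control or the pooled frequency.
- Keep the remark about more frequent variants only if it is attached to the corrected OR. At OR 1.8, for example, power is 99.7% to 99.9% at MAF 0.2.
- State the OR grid actually run, since the one described starts at 2.0 and contains neither 1.3 nor the corrected value.

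The cost is one rerun of the power script and changes to one bracket and one sentence. The stated detectable effect becomes less favourable; sample size, threshold and analysis stay as they are.

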## 6.2 Data analysis

The statistical analysis of this study will be conducted in collaboration with Human Technopole.

The primary analysis will follow a rigorous approach based on genome-wide regression models between germline variants and the presence of advanced MASLD. REGENIE software will be used, which allows for the evaluation of large-scale whole-genome regression in large genome-wide association studies. The secondary analysis involves the development and risk stratification by constructing polygenic risk scores specific to advanced MASLD and its subphenotypes.

The statistical analyses of the study will be conducted using R and Python software.

## 7. ADVERSE EVENTS

The project does not involve the administration of drugs or other substances, nor does it involve invasive clinical procedures. Therefore, no adverse events are expected.

## 8. RISK/BENEFIT ASSESSMENT

This study does not anticipate an immediate benefit to participants, but the results will be fundamental for the identification of specific therapeutic targets and for the development of new personalized medicine strategies.

## 9. STUDIO MANAGEMENT

### 9.1 Data collection and management

Each participant will be assigned a unique code upon enrollment. Data de-identification will be performed in such a way that people accessing the database will not be able to trace the subjects' identities in any way. Only local investigators will be able to trace the identities of enrolled subjects. The data required for the study will be recorded in a dedicated eCRF in a Data Management System validated according to national regulations, provided by the Foundation's Scientific Directorate. The platform used will be RedCap (Research Electronic Data Capture).

The REDCap Consortium is composed of >1,000 institutional partners worldwide (research institutions, universities, ministries, etc.). The consortium supports a secure web application

(REDCap) designed exclusively to support data acquisition for research studies. The REDCap application allows users to quickly and securely create and manage online databases and is currently in use for more than 110,000 projects with approximately 150,000 users covering numerous research areas across the consortium.

Through REDCap, this study will implement: a) user-level identification, with specific restrictions based on role in the study b) real-time data validation and integrity checking c) patient de-identification before data export d) centralized data storage with daily backup, on a secure server within the Foundation's IT infrastructure.

## **9.2 Regulatory aspects and ethical considerations**

### **9.2.1 Approval by the Competent Authority**

In accordance with applicable regulations, the principal investigator must obtain approval from the appropriate Competent Authority before initiating the clinical study.

This study will be conducted in accordance with ICH/GCP (International Conference on Harmonization/Good Clinical Practice) regulations and all applicable laws, including the Helsinki Declaration of June 1964, as amended by the last World Medical Association General Assembly in Seoul, 2008.

### **9.2.2 Ethics Committee Approval**

The investigator must ensure that the protocol has been reviewed and approved by the local independent Ethics Committee (EC) before starting the study.

The CE must also review and approve the informed consent (IC) form and all written information received from the patient prior to enrollment in the study.

Should it be necessary to modify the protocol and/or the IC during the study, the investigator will be the guarantor and therefore the person responsible for ensuring the review and approval of such modified document as requested by the CE.

The content of these changes will be implemented only after the EC has approved them. Until then, it will be necessary to refer to the previous version of the already approved document.

### 9.2.3 Informed consent (IC)

The investigator or other personnel designated by him are responsible for informing the subjects about all aspects and procedures of the study.

Informed consent will be collected by the doctor during the visit.

The informed consent process must comply with applicable regulatory procedures. The investigator (or designated staff member) and the subject must date and sign the informed consent form before the patient begins any study-related procedures. The subject will receive a copy of the informed consent, dated and signed by both parties; the original copy will be retained in designated study archives. Neither the investigator nor designated staff member may in any way coerce or influence a subject to participate or continue participating in the study. A subject's decision to participate in the study must be completely voluntary. The investigator and designated staff member must emphasize to the subject that they may withdraw their consent at any time without penalty or loss of any benefits to which they may be entitled.

Written or oral information relating to the study, including the written consent form, must not contain any language that forces the subject to waive (even apparently) his or her legal rights, or that would exonerate the investigator, institution, or sponsor from liability for negligence.

If participant access to the Foundation is not foreseeable within a timeframe compatible with the conduct of the study, given that this study requires the use of biological samples previously biobanked at the Foundation (patients have consented to the preservation of biological material for future research activities), consent to participate in the study, and the related data processing, may be obtained remotely via telephone.

During the telephone call, the Investigator, or a delegate, will provide the participant with information about the study and data processing methods, answer any questions, and verify the email address to which study documentation should be sent. The telephone call will be tracked using the document "INSTRUCTIONS AND FORM FOR ACQUIRING CONSENT BY

TELEPHONE CALL - PARTICIPATION IN CLINICAL TRIALS," which will be archived with the study documentation.

### **9.3 Duties of the investigator**

In accordance with applicable local regulations, the investigator must submit periodic reports regarding the progress of the study at his/her site to the CE and notify the CE of study closure. Periodic reports and closure notification are the investigator's responsibilities.

### **9.4 Study monitoring**

In accordance with applicable regulations and Good Clinical Practice (GCP), the monitor must periodically visit or contact the center. The duration, nature, and frequency of these visits/contacts depend on the recruitment rate, the quality of the center's records, and their adherence to the protocol.

Through these contacts, the monitor must:

- monitor and evaluate the progress of the study
- examine the collected data
- conduct the verification of the source document
- identify each problem and related solutions

The purposes of the monitoring activity are to verify that:

- the rights and well-being of the subject are respected
- the study data are accurate, complete and verifiable from the original documents
- the study is conducted in accordance with the protocol and any approved amendments, GCP and applicable regulations

The experimenter must:

- give the monitor direct access to all relevant documentation
- dedicate part of his time and his staff to the monitor to discuss the monitoring results and any other possible aspects.

The monitor must also contact the center prior to the start of the study to discuss the protocol and data collection procedures with the staff.

## **9.5 Study quality assurance**

As the sponsor, Fondazione IRCCS Ca' Granda, Ospedale Maggiore Policlinico may conduct a quality control review of the study at its discretion. In this case, the investigator must allow the monitor direct access to all relevant documentation and dedicate part of their time and staff to the reviewer to discuss the monitoring results and any other aspects of the study.

Additionally, Regulatory Authorities may conduct inspections. In this case, the investigator must grant the inspector direct access to all relevant documentation and dedicate part of their time and personnel to the inspector to discuss the monitoring results and any other aspects of the study.

## **9.6 Closure of the study**

Upon study closure, the monitor and the investigator must activate a series of procedures:

- review all study documentation
- reconcile study data
- reconcile all clarifying reports.

## **9.7 Document storage**

In accordance with current national regulations, the investigator must retain a copy of all documentation and store it in a dry, safe place after the study has been closed.

## **9.8 Disclosure of information regarding scientific discovery**

### **9.8.1 Confidentiality**

The investigator and other personnel involved in the study must maintain all information related to the study (including the protocol, data obtained, and all documentation produced during the study) and must not use such information, data, or reports for purposes other than those

described in the protocol. These restrictions do not apply to:

- 1) information that becomes publicly available, not due to negligence on the part of the investigator or his staff;
- 2) information requiring confidential disclosure to CE for the sole purpose of evaluating the study;
- 3) information that must be disclosed in order to obtain appropriate medical care for a study subject.

#### 9.8.2 Publications and Intellectual Property Rights on the Results of the Study

##### **a) SINGLE-CENTER STUDY which includes collaborations:**

###### **Publications:**

As the Promoter, the Foundation will ensure the dissemination and publication of the study results, even in the event of negative results, without any restrictions and guaranteeing the collaborating center visibility proportional to its actual participation.

Each scientific journal or publication containing the study results and data must indicate the role and participation of the collaborating center and the Foundation, in proportion to their actual contribution to the study and their role. The data may be published in aggregate form or otherwise anonymized, so as not to allow the identification of the data subject.

